#### 6.3. Other Endpoints

#### 6.3.1. Skin Irritation Score

For each subject, the maximum irritation score of the skin irritation assessment through all visits (ie, Day 3 and Day 4) will be calculated.

For the maximum irritation score, the frequency (number and %) of individual maximum irritation scores will be presented for each investigational product. The descriptive statistics (n, number of missing, mean, standard deviation, median, minimum and maximum) of the maximum irritation score will also be calculated for each investigational product.

For the irritation score, the frequency (number and %) of individual irritation scores will be presented for each investigational product at each visit. The descriptive statistics (n, number of missing, mean, standard deviation, median, minimum and maximum) of the irritation score will also be calculated for each investigational product at each visit.

Individual irritation scores will be displayed in a data listing for all subjects.

#### **6.4. Subset Analyses**

Not Applicable

## 6.5. Baseline and Other Summaries and Analyses

#### 6.5.1. Baseline Summaries

For Cohort 1, descriptive summary reports for demographic and baseline characteristics (age, gender, ethnicity, race, weight, height and body mass index) will be provided for the safety analysis population. For cohort 2, descriptive summary reports for demographic and baseline characteristics (age, gender, ethnicity, race, weight, height, body mass index, investigator's static global assessment score and treatable % BSA) will be provided by treatment for the safety analysis population.

Medical history will be summarized for Cohort 1, and by treatment for Cohort 2, for the safety analysis population.

Data will be reported in accordance with the Pfizer data standards.

## 6.5.2. Study Conduct and Subject Disposition

Subject evaluation groups will show end of study subject disposition and will show which subjects were analyzed for pharmacokinetics (for Cohort 2 only) and safety. Frequency counts will be supplied for subject discontinuation(s) for Cohort 1, and by treatment for Cohort 2.

Data will be reported in accordance with the Pfizer data standards.

## 6.5.3. Study Treatment Exposure

The administration schedule (duration of treatment, total number of applications) will be summarized descriptively by treatment, separately for each cohort for the safety analysis population.

Data will be reported in accordance with the Pfizer data standards.

## 6.5.4. Concomitant Medications and Non-Drug Treatments

All prior and concomitant medication(s) as well as non-drug treatment(s) will be summarized for Cohort 1, and by treatment for Cohort 2, and provided in the listings.

## 6.6. Safety Summaries and Analyses

Physical examination information collected during the course of the study will be considered source data and will not be required to be reported. However, any untoward findings identified on physical examinations conducted during the active collection period will be captured as AEs, if those findings meet the definition of an AE. Data collected at screening that are used for inclusion/exclusion criteria, such as laboratory data, ECGs, and vital signs, will be considered source data, and will not be required to be reported.

The statistical analysis for adverse events, labolatory data, vital signs and ECG are described in Section 6.1.

#### 7. INTERIM ANALYSES

## 7.1. Introduction

No formal interim analysis will be conducted for this study. However, for Cohort 1, as this is a sponsor open study, the sponsor may conduct unblinded reviews of the data during the course of the study for the purpose of safety assessment, skin irritation assessment, and/or supporting clinical development.

## 7.2. Interim Analyses and Summaries

Not Applicable.

## 9. APPENDICES

# **Appendix 1. DATA DERIVATION DETAILS**

Definition and use of visit windows in reporting

For cohort 2, the visit windows below will be used for any safety summaries that display by visit.

## **Definition of Visit Windows**

Visit Label	Target Day	Definition [Day window]
Day 1	Prior to Day 1, start of study treatment	Day 1
Day 8/ET	Day 8	Day 2 or later

If two or more visits fall into the same window, keep the one closest to the Target Day. If two visits are of equal distance from the Target Day in absolute value, the later visit should be used.

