### Final Protocol Amendment 1, 14 July 2017

- a. Day relative to start of study treatment (Day 1).
- b. Follow-up contact will be completed on Day 29 (28+7 calendar days after the application of the investigational product patches on Day 1) to capture any potential adverse events.
- c. Subjects will be admitted to the Clinical Research Unit (CRU) on Day -1.
- d. Subjects will discharge from CRU on Day 4 after completion of all assessment on Day 4.
- e. Day -1 clinical labs do not have to be repeated if clinical labs are completed within 7 days prior to Day -1.
- f. Vital signs (pulse rate and blood pressure) taken supine position after subject has been calmly lying for 5 minutes.
- g. Single ECG will be collected.
- h. Day -1 urine drug testing does not have to be repeated if urine drug testing is completed within 7 days prior to Day -1.
- i. Day 1 patches remains in place through Day 3.
- j. Skin irritation assessment of the patch sites will be conducted on Day 3 (approximately 30 minutes after removal of the patches) and Day 4 (approximately 24 hours after removal of the patches).
- k. All medications and non-medication therapies used within 28 days prior to the planned first dose.
- 1. If AEs/SAEs occur at a patch site, the patch site location must be recorded.

Day a	−28 to −2	-1	1	2	3	4	5	6	7	8/ET	9	36 (+7 days)
•	Screening											FU Contact b (EOS)
Informed Consent	X											
CRU confinement		X c	$\rightarrow$	$\rightarrow$	$\rightarrow$	$\rightarrow$	$\rightarrow$	$\rightarrow$	$\rightarrow$	$\rightarrow$	$X^{d}$	
Inclusion/Exclusion Criteria	X	X	X									
Medical History	X	X										
Confirmation of Diagnosis of AD	X											
Physical Examination	X	X								Xe	X	
Physical Examination (skin examination)	X		X								X	
Assess ISGA	X		X									
Record treatable AD areas			X									
Calculate and Record Treatable %BSA g	X		X									
Safety laboratory	X	X								X		
Demographics	X											
Height and Weight	X		X h									
Vital Signs i	X		X							X		
ECG	$\mathbf{X}^{\mathrm{j}}$		$\mathbf{X}^{\mathbf{j}}$							X j		
Urine Pregnancy test	X	X										
Contraception check	X	X									X	X
FSH k	X											
HIV, HepBsAg, HepBcAb, HCVAb and syphilis testing	X											
Urine drug testing	X	X										
AM Dosing: Weigh dose and apply			X	X	X	X	X	X	X	X		
PM Dosing: Weigh dose and apply				X	X	X	X	X	X			

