# 6.2.2.1. Day -1

Subjects will be admitted to the CRU at least the day prior to Day 1 dosing. The following procedures will be completed following admission to the CRU:

- Review inclusion and exclusion criteria;
- Obtain blood and urine samples for safety laboratory tests. The results must have no clinically significant findings, as judged by the investigator, in order for a subject to be given investigational product on Day 1;
- Collect urine for drug testing. Do not have to be repeated if urine drug testing is completed within 7 days prior to Day –1;
- Collect urine pregnancy test for female subjects of childbearing potential;
- Confirm highly effective contraception is being used for female subjects of childbearing potential;
- CC
- Assess baseline symptoms/AEs;
- Review changes in the subject's medical history, including medication history since screening;
- Conduct physical examination except skin examination.

# 6.2.2.2. Day 1

**Prior to dosing**, the following procedures will be completed:

- Review inclusion and exclusion criteria;
- Conduct physical examination for skin examination;
- Complete the ISGA (the ISGA score must be 2 or 3 on Day 1 for subject to be eligible);
- Record treatable AD areas;
- Calculate and record Treatable %BSA;
- Assess baseline symptoms/AEs;
- Collect weight;
- Collect 12-lead ECG measurements prior to insertion of the IV catheter;
- Collect supine BP and PR prior to insertion of the IV catheter;
- Collect a blood sample for PK analysis at predose;
- Review and record prior medications;
- After all predose procedures have been completed, apply the investigational product (see the Administration section);
- AM application: wearing gloves, study site staff will apply the calculated amount of study drug (per application dose) to all treatable AD lesions identified on Day 1;
- Collect blood samples for PK analysis at 3 and 12 hours following application on Day 1;
- Assess symptoms by spontaneous reporting of AEs and by asking the subjects to respond to a nonleading question such as "How do you feel?"

# 6.2.2.3. Day 2

The following procedures will be completed:

- Collect blood samples for PK analysis at 24 hours following application on Day 1;
- Review and record concomitant medications:

- AM application: wearing gloves, study site staff will apply the calculated amount of study drug (per application dose) to all treatable AD lesions identified on Day 1;

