It may be appropriate for the subject to return to the clinic for final safety assessments to be scheduled as early as practically feasible following the decision to withdraw from the study. Subjects should be questioned regarding their reason for withdrawal. At the early-withdrawal visit, every effort must be made to complete the following assessments:

#### Cohort 1

- Review and record concomitant medications.
- Assess the skin irritation response of the patch sites.
- Conduct physical examination
- Assess symptoms by spontaneous reporting of AEs and by asking the subjects to respond to a nonleading question such as "How do you feel?" If AEs/SAEs occur at a patch site, the patch site location must be recorded.

#### Cohort 2

- Review and record concomitant medications.
- Collect 12-lead ECG measurements prior to insertion of the IV catheter.
- Collect supine BP and PR prior to insertion of the IV catheter.
- Obtain blood and urine samples for safety laboratory tests.
- Collect a blood sample for PK analysis.
- Conduct physical examination
- Assess symptoms by spontaneous reporting of AEs and by asking the subjects to respond to a nonleading question such as "How do you feel?"

Lack of completion of all or any of the withdrawal/early termination procedures will not be viewed as protocol deviations so long as the subject's safety was preserved.

If the subject withdraws from the study and also withdraws consent for disclosure of future information, no further evaluations should be performed and no additional data should be collected. The sponsor may retain and continue to use any data collected before such withdrawal of consent.

Subjects who withdraw from the study may be replaced at the discretion of the investigator upon consultation with the sponsor.

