#### 6.1.3. Laboratory Data

Laboratory data are one of the primary endpoints for Cohort 2. The analysis of laboratory data will be based on the safety analysis population. Laboratory data will be descriptively summarized and listed by treatment in accordance with the Pfizer data standards. Baseline will be the last predose measurement.

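### The Cohort 2 visit windows are cut by calendar day, so a post-dose ECG or blood-pressure reading on Day 1 falls in the pre-treatment window and cannot reach Day 8/ET

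*SAP*

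**What the plan says.** SAP Appendix 1 states that for Cohort 2 "the visit windows below will be used for any safety summaries that display by visit". Its table has two rows.

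- Day 1: the target is "Prior to Day 1, start of study treatment", and the window is calendar Day 1, with no predose condition and no earlier days.
- Day 8/ET: the target is Day 8, and the window runs from Day 2 onward.

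When several visits share a window, the one nearest the target is kept. The tie rule is: "If two visits are of equal distance from the Target Day in absolute value, the later visit should be used".

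SAP 6.1.4 (vital signs) and 6.1.5 (ECG) both call for summaries by treatment and visit, so the windows govern them. SAP 6.1.3 is worded differently: "Laboratory data will be descriptively summarized and listed by treatment in accordance with the Pfizer data standards". It does not mention visit.

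For baseline, SAP 6.1.3 says "Baseline will be the last predose measurement", and 6.1.4 says the same for vital signs. SAP 6.1.5 reports changes from baseline for ECG but does not define that baseline. Protocol 7.1.5 and 9.5.1 do not define it either.

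In the Protocol's Cohort 2 schedule, blood pressure, pulse rate and ECG are taken at Screening, on Day 1 before dosing, and on Day 8 or at early termination. Safety laboratory tests are taken at Screening, on Day -1 (Protocol 6.2.2.1: "Obtain blood and urine samples for safety laboratory tests") and on Day 8 or at early termination. None is scheduled on Day 1.

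**The concern.** Day 1 contains both the last untreated reading and the first hours of exposure. A window meant to hold the untreated value needs a boundary at the first application, and this one has its boundary at midnight. Any post-dose reading on Day 1 is therefore grouped with the predose reading, and the window meant for on-treatment values cannot accept it.

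Vital signs and ECG are Cohort 2 primary endpoints (SAP 3.1), summarised descriptively in about 10 crisaborole and 2 vehicle subjects. A subject withdrawn on Day 1 would have no on-treatment entry in those tables. On one reading of the tie rule, that subject's post-dose value would also sit in the row a reader takes as pre-treatment.

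The ECG section carries a further exposure. With no stated baseline, a programmer could take the windowed Day 1 record as baseline, and the misplacement would then pass into change from baseline.

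**Working it through.** No figure in the plan needs reproducing. The check applies the window definitions as written to each Cohort 2 safety assessment, and then to the unscheduled cases that the Protocol allows.

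**Step 1. Which tables are affected.** Vital signs and ECG are summarised by visit (SAP 6.1.4, 6.1.5). For laboratory data a by-visit display is not stated (SAP 6.1.3).

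**Step 2. Assignment.**

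| Assessment | Window as written | Window if split at first application |
|---|---|---|
| BP/PR, ECG, Day 1 predose | Day 1 | Baseline/Day 1 |
| BP/PR, ECG, Day 8 | Day 8/ET | Day 8/ET |
| Early termination on Day 2 or later | Day 8/ET | Day 8/ET |
| Early termination on Day 1, post-dose | Day 1 | Day 8/ET |
| Laboratory panel, Day -1 | none | Baseline/Day 1 |
| Laboratory panel, Day 8 | Day 8/ET | Day 8/ET |

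Two rows change: the post-dose Day 1 termination, and the Day -1 laboratory panel. The second matters only if laboratory data are tabulated by visit.

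**Step 3. Can a post-dose Day 1 reading occur?** Protocol 6.4 sets no earliest day for the early-termination visit, and that visit includes ECG ("Collect 12-lead ECG measurements prior to insertion of the IV catheter"), blood pressure, pulse rate and laboratory tests. Protocol 7.1.4 permits extra blood pressure and pulse rate measurements, and the Schedule of Activities permits unplanned visits. No post-dose ECG or blood pressure is scheduled on Day 1. The case is possible but not routine.

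**Step 4. What the closest-visit and tie rules do with it.** There are two ways to measure distance from the first row's target.

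- Counted in days: the predose and post-dose readings are both on Day 1, so they are equally far from the target, whether that is taken as Day 1 (distance 0 for both) or the day before. They tie and the later one is kept. The post-dose reading fills the Day 1 row and the predose reading is dropped.
- Counted from the moment before treatment: the predose reading is nearer and is kept. The post-dose reading is dropped from the table.

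On both readings the post-dose value is absent from Day 8/ET, and a subject who terminated on Day 1 has no entry there. A subject who has an unscheduled Day 1 reading but stays to Day 8 still has a Day 8/ET value. For that subject the only damage is the displaced predose reading, under the first way of counting.

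**Step 5. Size.** The 5:1 allocation of 12 subjects gives 12 × 5/6 = 10 crisaborole and 12 × 1/6 = 2 vehicle. One crisaborole termination on Day 1 leaves 10 − 1 = 9 subjects under Day 8/ET, a loss of 1/10 = 10% of that arm. This is the arithmetic of one assumed case; the documents give no probability for it. If laboratory data were shown by visit, 0 of 12 scheduled Day -1 panels would fall in a window.

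**Step 6. Does it reach baseline?** For vital signs and laboratory data it does not, because baseline is the last predose measurement whatever the windows say. For ECG the text leaves it open. The categories of maximum post-dose QTc are not by-visit and are untouched. The categories of maximum increase are not windowed either, but they use whatever ECG baseline is adopted.

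**The case against.** The strongest reply is that the scheduled data are handled correctly. The two endpoints expressly shown by visit both have a Day 1 predose assessment. The version 2.0 change log in the SAP fits this: it lists 6.1.4, 6.1.5 and the new windows, and does not list 6.1.3. A Day 1 early termination is also unlikely. Under Protocol 6.4 a subject who only stops treatment stays in the study, Cohort 2 subjects are confined until Day 9, and the visit would have to fall on the same day as the single Day 1 application. The first row's target also shows that a pre-treatment value was meant, and a reader who measures distance from that moment never reaches the tie rule.

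Most of this stands, and it limits the point to a minor one. It does not remove it. Even on the reading that keeps the predose value, the post-dose value is discarded instead of moving to Day 8/ET.

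A reader might go further in two ways that the documents do not support.

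- One could infer that all baseline laboratory data are lost and that Appendix 1 contradicts SAP 6.1.3. It does not. Appendix 1 does not define baseline; 6.1.3 defines it independently, so the Day -1 panel remains the scheduled laboratory baseline for all 12 subjects. A gap arises only if laboratory data are tabulated by visit under the sponsor's data standards, which are not part of the documents.
- One could infer that an acute reaction would be reported as an abnormal baseline and so be hidden. For vital signs and laboratory data the baseline sentences rule that out. The AE summaries, the listings and the maximum post-dose QTc table would still show the event.

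**Conclusion.** The rule is wrong as written, and the consequence is minor. The calendar-day definition does not carry out the row's pre-treatment target, so a post-dose Day 1 blood pressure, pulse rate or ECG reading is grouped with pre-treatment values and excluded from Day 8/ET. If distance is counted in days, it also replaces the predose reading.

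The effect is confined to the by-visit vital-sign and ECG tables and needs a Day 1 termination or an unscheduled post-dose reading that day. One termination would be 1 of 10 crisaborole subjects. The missing ECG baseline definition is the one route by which the error could spread to change from baseline. The laboratory gap is conditional on a by-visit display that SAP 6.1.3 does not state. The study tests no hypotheses (SAP 5.1), so no inferential result is affected.

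**What to change.** In SAP Appendix 1:

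- Define the first window as the last measurement before the first application, including Day -1 or earlier.
- Define Day 8/ET as any measurement after the start of the first application, including later on Day 1.
- Apply the closest-visit and tie rules only within the post-dose window.

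In SAP 6.1.5, state that ECG baseline is the last predose measurement, matching 6.1.3 and 6.1.4.

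The cost is two table cells, a qualifier on the tie rule and one sentence. No assessment is added, and the Day 1 predose readings, the Day 8 readings and early terminations from Day 2 onward keep their present windows. Programming needs Day 1 readings to be identifiable as before or after dosing. Protocol 5.7.2.1 already relies on a recorded completion time for the Day 1 application. I assume that measurement times, or a predose/post-dose label, are also captured.
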